These items were collected by self-report in the CAST study. The selection of these variables as outcome indicators is supported by evidence from van Rijn³⁰ who reported recovery was most closely associated with improvements in pain and giving way. Wikstrom et al⁴ report pain and instability are of greatest concern to patients. We have examined the CAST data set and the event rate is 30%. Given the event rate and number of predictors we will carry forward, we have more than adequate numbers for modelling.

Internal validation, score and format derivation

We will internally validate the models using bootstrapping, and adjust for over fitting. We will simplify the presentation of various models to a scoring system.^{23,31} This can be more challenging than initially appears, but we will enlist the help of our PPI reps and clinical colleagues in developing a rational tool for clinical/patient self-completion.

The prognostic models will produce a risk score (probability) for each patient. The statistical measures of calibration or discrimination do not capture the clinical usefulness of the prediction model (i.e. how does using the prediction model improve on a default policy of no prediction

model). This will be examined using decision curve analysis, which calculates the net benefit of using the model compared to not using the model,³² evaluating and determining ranges of cut-off values for decision-making.

Ethics

The CAST study had full ethical and other approvals, and the consent taken covers the intended use of the data.

Stage 2 – Evidence synthesis from literature and expert consensus process to refine prognostic tool

The CAST data set whilst comprehensive is not exhaustive. For example, we included some physical examination tests, but there are alternative tests available and since CAST was completed, technologies around gait assessment have moved on considerably. Scoping searches completed (see section Existing Research) do not suggest major deviation from the variables collected in CAST, however we cannot (and should not) rule out the need to collect additional variables.

2a – systematic review

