The participants will be a maximum of 12 clinicians (including ED doctors, trauma/sports physicians, physiotherapists, ED nurses, and minor injury unit staff), and 12 patients (representing a range of age, gender and physical activity/sport participation). The tool will then undergo final revision and common sense testing before release for external validation. Our plan will be to present two schedules of data collection for completion (excluding data on sample characteristics that are not contained in either schedule). The first will be prognostic tool as generated by the development data set. These will require a degree of formatting to convert data collected in a clinical research form, to an easy to complete prognostic tool. The additional predictive factors will also be formatted in a similar and completely complementary manner, but collected on the separate schedule (and after completion of the primary tool). The two schedules will be collected by the same clinician. In this way if any of the additional factors is confirmed as important, we will add them into the final tool, causing least disruption to the process of validation. If there is more than one additional predictive factor, we will randomise the order of data presentation across participants to gain insight into whether the order or opportunity to provide additional data in anyway biases the sample.

All participants of the consensus exercise will provide consent to participate. PPI members will be paid for their time and contribution, clinicians will not.

Stage 3: Externally validate and optimise the tool in a new cohort of patients recruited from NHS Emergency Departments

We will externally validate the prognostic tool developed in stages 1 and 2 in a new prospective cohort. We will recruit 675 people from 5 EDs, from a pool of 7,500 to 10,000 ankle sprains per annum at a conservative rate of 15 sprains per centre per month. We have provisional agreement from an additional 5 EDs to participate if required.

We cannot be completely certain of how this element of the study will run, as this will vary depending on the final tool. We have at this stage assumed that the tool will require contact at initial attendance and one early follow up visit (at around 5 days), and will include a mix of self-report and clinical tests. We have considered a range of other possibilities, and can provide these if needed.

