Depending on the final format, the patient or ED clinicians (or both) will be asked to complete the prognostic tool. Although the predictor variables may be evident as per usual clinical practice, the prognosis will not be computed until final 9 month follow up is complete for each participant. Clinicians will be asked to continue to manage patients within the normal pathways at each of their hospitals, and we will record resource use. We may ask participants to return to the site, or complete some self-tests at home if further examination is indicated.

The questionnaires collected from participants at 4 and 9 months and will include details of severe and persistent symptoms, instability (as previous discussed), the validated Foot and Ankle Outcome Score,³⁹ health service resource use during follow up, and health related quality of life. Participants will be able to choose to respond via the web or a postal questionnaire. Additional demographic information will be collected if this is not included in the prognostic tool (for example sprain severity, age, gender, employment status). We are unlikely to include imaging techniques as either a component of the prognostic tool, or during follow up, although we will record if an image is taken and used in the practice. There is no indication in the literature that imaging adds to prognostic information, although a study of low dose CT scanning is being completed by one of the co-applicants of the study.

Sampling: The same principles apply to the sample size calculation stated here, as in Stage 1 justification for modelling. Current recommendations are that a minimum of 100 outcome events are required for external validation.^{24,40} We anticipate the event rate to be between 26% and 32%, this would require an overall sample size of between 313 and 385. Assuming a 25% loss to follow-up and a lower event rate (20%) when recruiting all grades of ankles sprains we will target 675 patients to ensure the event rate is achieved.

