Analysis: The performance of the tool will be assessed using calibration and discrimination metrics. Calibration will be assessed graphically with results for patients grouped by similar probabilities (tenths) and compare the mean predicted probability to the mean observed outcome.^{23,24} The calibration plot will also be supplemented with estimates of the calibration slope and intercept. The discrimination of various prognostic models will be summarised with the concordance index (equivalent to the Area Under Receiver Operating Characteristic curve) with 95% confidence interval. Additional predictors not contained in the development dataset will be examined to see whether they improve the performance of the prognostic model using net reclassification improvement (NRI) and integrated discrimination improvement (IDI).⁴¹

Neither calibration nor discrimination captures the clinical usefulness of the prediction model (i.e. how does using the prediction model improve on a default policy of no prediction model). This will be examined using decision curve analysis, a relatively novel yet increasingly recommended approach in evaluating the predictive performance of a prediction model. It calculates the net benefit of using the model compared to not using the model,³² evaluating and determining ranges of cut-off values for decision-making. The approach permits evaluation of the tools over a range of thresholds and the model with the greatest net benefit (i.e. the number of true positives penalised by a weighted proportion of the false-positives) will be considered as the preferred prediction model. The results will be converted into 'an additional x patients per 1000' who would be identified using the prediction tool compared to not using the tool. If additional predictors are found to be helpful, we will evaluate the incremental value of the predictors and update the model to accommodate these accordingly.^{23,31} A model with the greatest net benefit (i.e. the number of true positives penalised by a weighted proportion of the false-positives) will be considered as the preferred prediction model.³²

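### NRI and IDI are a poor screen for predictors added in Stage 3: both are biased upward for noise, worst when several are added together, and both have less power than a likelihood-ratio test

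*Protocol*

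**What the plan says.** Under the Analysis paragraph of Stage 3 in the protocol, candidate predictors that CAST lacks are to be studied in the new cohort "to see whether they improve the performance of the prognostic model using net reclassification improvement (NRI) and integrated discrimination improvement (IDI". No other measure is assigned to that question. The consequence follows in the next paragraph: "If additional predictors are found to be helpful, we will evaluate the incremental value of the predictors and update the model to accommodate these accordingly". Stage 2b, on the consensus process, points the same way: "if any of the additional factors is confirmed as important, we will add them into the final tool".

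The choice between models is a separate, later rule. The model with the greatest net benefit "will be considered as the preferred prediction model". The same section also plans a calibration slope and intercept, and a c-index with a 95% confidence interval.

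Bootstrapping with adjustment for overfitting is stated for Stage 1 (internal validation). Nothing equivalent is stated for the added-predictor step. The protocol does not say whether the comparator is the CAST model as developed, a recalibrated CAST model or a refitted one, nor which version of NRI is meant.

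**The concern.** A predictor that CAST did not collect has no CAST coefficient. Its weight has to be estimated in the Stage 3 cohort and then judged on the same patients. NRI and IDI computed that way have no built-in allowance for the extra fitted parameter, so they tend to be positive even when the predictor carries no information. A likelihood-ratio test makes that allowance through its degrees of freedom.

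At stake is the content of the released tool. A screen that leans toward noise lengthens the tool for no gain, and a screen with low power can discard a useful item before net benefit is considered.

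**Working it through.** **Protocol inputs.** Stage 3, Sampling: 100 events required, event rate anticipated at 26% to 32% with an allowance for 20%, 25% loss, target 675. Stage 1: CAST event rate 30%, and 441 to 584 patients with follow-up depending on the time point.

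**The plan's own figure.** 100/0.32 = 313 and 100/0.26 = 385, as stated. 100/0.20 = 500 and 500/0.75 = 667, close to the 675 stated. The cohort for analysis is then 675 × 0.75 = 506, with 0.20 × 506 = 101 events.

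**Assumptions not in the protocol.** The linear predictor has SD 0.8 (c-index about 0.69), with a check at SD 1.2 (about 0.77). Where a CAST-like development sample is simulated, it has n = 441 and 8 predictors. NRI cut-offs, where used, are 0.2 and 0.4. Performance is measured on the data used for fitting, because no correction is stated. Monte Carlo error is about 2 percentage points.

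**Measures.**
- Category-free NRI = [P(risk up | event) − P(risk down | event)] + [P(risk down | no event) − P(risk up | no event)].
- IDI = mean change in predicted risk in events − mean change in non-events.
- Likelihood-ratio statistic = 2(log L extended − log L base), referred to chi-square with as many degrees of freedom as predictors added.

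**Pure noise added to a recalibrated or refitted base**

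| Result | 1 noise predictor | 3 added jointly |
|---|---|---|
| Category-free NRI above 0 | 79-82% | 95-96% |
| IDI above 0 | 88-94% | 99% |
| NRI with cut-offs above 0 (refitted base) | 52-57% | 71% |
| NRI z > 1.96 (nominal 2.5%) | about 6-7% | 22-25% |
| IDI z > 1.96 (nominal 2.5%) | about 3-4% | 21-23% |
| Likelihood-ratio test rejects (nominal 5%) | about 5% | about 5% |

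The mean category-free NRI is about +0.07 to +0.08 with one noise predictor and about +0.15 to +0.16 with three.

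**A useful predictor, recalibrated base.** With an odds ratio of 1.42 per SD, power is about 85% for the likelihood-ratio test, 79% for IDI and 70% for NRI.

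**If the comparator were the uncorrected CAST model.** In a sample of 1,000,000 with no new predictor and unchanged ranking of patients, a fall from 30% to 20% placed wholly in the intercept gives:
- IDI −0.023
- NRI with cut-offs −0.055
- category-free NRI 0.000

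For scale, a real predictor with odds ratio 1.3 per SD, calibrated against calibrated, gives +0.011, +0.037 and +0.213 respectively. The IDI artefact is thus about twice that signal (0.023/0.011) and opposite in sign.

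In cohorts of 506 with the predictor of odds ratio 1.42, the result depends on where the fall comes from:
- All in the intercept: IDI is significantly positive in 12-15% and significantly negative in 23-28%.
- Carried by the model's own predictors: 62% and 3%.
- Event rate 28%: 60% and 3%.

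**The case against.** **Net benefit is the final rule.** This stands in part. NRI and IDI do not alone decide what enters the tool. But net benefit cannot recover a predictor already dropped at the screen, and no optimism correction is stated for it either. At an assumed 20% threshold, a model with one noise predictor still beats the recalibrated base on net benefit in about half of simulated studies.

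**For one predictor the tests are nearly sound.** This stands. False inclusion of about 6% (NRI) or 4% (IDI) is close to the 5% of a likelihood-ratio test. The 80% figure is the share of positive signs, and the protocol has no rule that a positive sign means inclusion. The serious inflation appears when several predictors are added together; Stage 2b allows for more than one.

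**Pure noise is unlikely to get this far.** Stage 2a asks for moderate or high risk replicated in more than one cohort, and a consensus group then reviews the candidates. This lowers the chance of a worthless addition but leaves the lower power untouched.

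**The SAP may settle comparator, NRI version and decision rule.** It may, and their absence here is not the point. The point is the pair of measures that the protocol itself names for this step.

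**Conclusion.** The point holds as a criticism of the screening measures. Against a recalibrated or refitted base, category-free NRI and IDI lean upward for noise. The error is mild for one predictor and large for three added jointly. Power for a useful predictor is about 6 (IDI) to 15 (NRI) percentage points below the likelihood-ratio test (85 − 79 and 85 − 70). NRI with cut-offs leans upward much less for a single predictor. The figures rest on n = 506, mainly 20% events, the assumed spread of the linear predictor and no optimism correction.

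A reader might go further and infer that these measures would mainly record miscalibration of the CAST model, so that a useful predictor would usually look harmful. The protocol does not support that. It never says that the uncorrected CAST model is the comparator. The 20% is an allowance ("lower event rate (20%) when recruiting all grades of ankles sprains") beside an anticipated 26% to 32%. Severity, weight bearing and pain are candidate predictors, so the model may explain part of any fall. Stage 1 also plans to adjust for overfitting. The safe statement is conditional: with an uncorrected comparator, IDI would mix the predictor's value with miscalibration, by an amount that the protocol does not determine.

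**What to change.** Replace the NRI and IDI sentence in the Stage 3 Analysis paragraph with:

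> The CAST linear predictor is first recalibrated (intercept and slope) in the Stage 3 cohort. Additional predictors are then added and judged by a likelihood-ratio test and by the bootstrap optimism-corrected change in c-index and net benefit. NRI and IDI, if reported, are descriptive only.

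This needs no new data and a little more analysis work. The c-index and net benefit are already planned; the additions are the recalibration, the test and the bootstrap correction.

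A multiplicity adjustment across several added predictors is optional and costs power. By normal approximation, 85% power at two-sided 5% corresponds to a shift of 1.960 + 1.036 = 2.996. With three predictors and Bonferroni, the level is 0.05/3 = 0.0167 and the critical value 2.394, so power is Φ(2.996 − 2.394) = Φ(0.602), about 73%.

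### A tool selected or extended in the Stage 3 cohort is measured on the patients used to choose or refit it, so its performance is optimistic and it has no external validation

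*Protocol*

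**What the plan says.** The Protocol's Aims and objectives give Stage 3 two jobs in one new cohort of 675: external validation and optimisation of the tool. The section on requirements of a prognostic tool makes external validation part of what makes a tool useful, and it criticises existing tools for lacking validation.

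The Stage 3 Analysis paragraphs then use the cohort in several ways:

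- Calibration (plot, slope, intercept) and the c-index are estimated. The text speaks both of the tool in the singular and of various models.
- Additional predictors absent from the development data are examined with NRI and IDI.
- Decision curve analysis is described as permitting "evaluation of the tools over a range of thresholds and the model with the greatest net benefit"; that model becomes the preferred one.
- If additional predictors turn out to be helpful, "we will evaluate the incremental value of the predictors and update the model to accommodate these accordingly".

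Stage 2b (Expert consensus process) says where such predictors go: "if any of the additional factors is confirmed as important, we will add them into the final tool".

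Correction for over-fitting is stated under Stage 1 only: "We will internally validate the models using bootstrapping, and adjust for over fitting". For Stage 3 the Protocol states no optimism correction, no split of the cohort and no second cohort.

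**The concern.** Choosing the best of several models, or estimating coefficients for new predictors, fits the result partly to chance features of the sample. Performance measured in that same sample is apparent performance, which on average is better than what new patients will show. External validation means testing a fixed model in patients who played no part in building it. A tool selected or updated in Stage 3 has not had that test.

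At stake is the study's main product. If the tool that goes forward is the preferred or extended one, the figures available for it from Stage 3 would be apparent values, including the net-benefit result that the Protocol plans to express as extra patients identified per 1000. The Protocol does not say which result is the primary validation result, nor that an updated tool would still need validating.

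**Working it through.** **1. The plan's own sample size (Stage 3, Sampling).** The basis is "a minimum of 100 outcome events are required for external validation". With N = events / event rate:

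- 100 / 0.32 = 312.5, so 313; 100 / 0.26 = 384.6, so 385. This reproduces the statement that "this would require an overall sample size of between 313 and 385".
- At the lower event rate of 20%: 100 / 0.20 = 500. Allowing for 25% loss: 500 / 0.75 = 667, against the stated 675 (1.2% apart).

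**2. What the cohort yields.**

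- Analysed: 675 × 0.75 = 506.
- Events at 20%: 506 × 0.20 = 101, one above the minimum. At 26% to 32%: 132 to 162.
- A half split would leave about 253 patients and 51 events for validation, about half the minimum. A fresh validation on the plan's terms would need about 667 more recruits.

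The cohort is sized for one validation and has no spare capacity for a second.

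**3. Optimism from adding predictors (simulation).** The Protocol gives no c-index, number of tools or number of added predictors, so these inputs are assumptions: 506 patients, 20% events, a correctly calibrated original score, m added predictors with no true effect, all refitted by logistic regression, 300 replicates, evaluation in 20,000 new patients, net benefit at a 20% threshold. The two values in each cell are for a true c-index of 0.65 and 0.73. Net benefit is per 1000.

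| m | Optimism in c-index | Slope in new patients (apparent 1.00) | Net benefit, apparent vs new |
|---|---|---|---|
| 1 | −0.001; 0.004 | 1.04; 0.99 | 44.0 vs 41.7; 66.3 vs 64.8 |
| 3 | 0.013; 0.009 | 0.94; 0.96 | 46.1 vs 39.5; 69.2 vs 63.7 |
| 5 | 0.024; 0.020 | 0.86; 0.90 | 46.0 vs 38.1; 70.2 vs 62.9 |
| 10 | 0.048; 0.037 | 0.71; 0.81 | 51.1 vs 35.1; 71.8 vs 60.1 |

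The −0.001 is simulation noise around zero.

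**4. Optimism from choosing among fixed tools (simulation).** K equally good tools, pairwise correlation 0.8 or 0.5, 506 patients, 20% events, choice by net benefit at a 20% threshold, 1,500 replicates. The gain is the chosen tool's value minus the average over the K tools.

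| K | Gain in c-index (correlation 0.8; 0.5) | Gain in net true positives per 1000 |
|---|---|---|
| 2 | 0.005; 0.010 | 4.1; 5.2 |
| 4 | 0.010; 0.018 | 7.2; 9.3 |
| 6 | 0.013; 0.022 | 9.0; 11.5 |

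Since the tools are equally good by construction, the whole gain is optimism.

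**The case against.** The strongest reply is that the Protocol already protects the validation that matters. The initial tool is to be finalised by the end of month 6, before recruitment (Project Timetables and Milestones). It is completed first, with additional factors on a separate schedule (Stage 2b), and scores are not computed until follow-up ends. Its Stage 3 calibration and c-index are therefore unbiased whatever happens later. This stands. It also rules out a stronger reading that a reader might infer, namely that the released tool will necessarily lack external validation. Updating happens only if predictors prove helpful. A single finalised tool released unchanged would be properly validated.

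Two further inferences are not supported. No passage says that an updated tool's performance will be presented as external validation. And the Stage 2b remark about disturbing the validation as little as possible concerns the order of data collection; it does not claim that an extended tool is validated.

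The size is also open to challenge, fairly:

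- Pure-noise predictors are pessimistic, because candidates must show moderate or high risk, be replicated in more than one cohort, and pass the consensus group.
- Appendix 1 lists only about four distinct items missing from the development data, so ten additions are unlikely.
- More than one tool entering Stage 3 is not certain. The consensus stage starts from a series of candidates, but later text speaks of one tool. Against that, a highest-net-benefit rule has no function with a single model.
- The 20% event rate is the plan's conservative case.

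Lastly, optimism correction could be specified in a statistical analysis plan that is not shown. Its absence alone is therefore no finding. But such a plan could not make a tool updated in Stage 3 externally validated, and it is the Protocol itself that sets the in-cohort choice and the entry of new factors into the final tool.

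**Conclusion.** The point holds for any tool selected by net benefit or extended with new predictors in Stage 3. Its apparent performance is optimistic, and it does not meet the Protocol's own criterion of external validation. It does not hold for the tool finalised beforehand and left unchanged.

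The lack of external validation for such a tool does not depend on any assumed number. The size of the optimism does. It is negligible to small (about 0.00 to 0.01 in c-index) for one to three noise predictors or a choice between two tools. With five noise predictors it is about 0.02, with predictions too extreme in new patients (slope 0.86 to 0.90). Choice among two to six equally good tools adds about 4 to 12 net true positives per 1000. These figures assume 506 analysed patients, a 20% event rate and, for net benefit, a 20% threshold. The Protocol states neither the number of tools nor the number of added predictors.

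**What to change.** In the Stage 3 Analysis section:

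1. Name one version of the tool finalised before Stage 3, and make its unmodified performance the primary external validation result.
2. For any tool selected or updated in Stage 3, bootstrap the whole procedure (choice of tool, choice of predictors, refitting) and report optimism-corrected c-index, calibration slope and net benefit.
3. Describe such a tool as updated and internally validated only, and state that it still needs external validation.

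This needs no new data and no larger cohort. The cost is wording, some bootstrap programming, and slightly less favourable figures for a selected or updated tool. Splitting the cohort is not a good alternative, since the validation half would have only about 51 events.
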